2.4 STUDY AIMS/HYPOTHESES

2.4.1 PRIMARY OBJECTIVE

NULL HYPOTHESIS. There is no difference in parasympathetic tone in Heart Rate Variability, shown by an increase in high frequency input via spectral analysis on EKG recordings between active and sham stimulation.

ALTERNATIVE HYPOTHESIS. There is a difference in parasympathetic tone in Heart Rate Variability, shown by an increase in high frequency input via spectral analysis on EKG recordings between active and sham stimulation.

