4 BASIC STUDY DESIGN

This study is a pilot clinical trial with a randomized, double-blind, crossover design. This is a single site study with 2 arms. We estimate six months to complete study enrollment.

Figure 1.

Active sham treatment will include 10 seconds of ramp-in to 1 minute of 10 Hz tACS with a ramp-out of 10 seconds for a total of 80 seconds of stimulation. The choice of an active sham is motivated to enhance success of patient blinding by mimicking skin sensations associated with tACS. 10 Hz tACS will have a 10 second ramp-in and ramp-out with 40 minutes of stimulation for a total of 2420 seconds of stimulation. Stimulation waveform is a sine-wave with peak-to-peak amplitude of 2 mA. In both arms, participants will stay in a relaxed yet controlled state by watching a nature movie (“Reefscape”) during stimulation.

Eligible participants who complete this clinical trial will have a total of 2 visits; 2 days of stimulation (with 1-3 weeks in between). Day one of stimulation will take approximately 2.5 hours as eligibility will be confirmed at the beginning. Day 2 of stimulation will take approximately 2 hours. Two days after each stimulation day, participants will receive via email a follow-up survey to complete that will take approximately 15 minutes. We estimate that total participation will be approximately 6 hours over the course of 6 weeks. All time estimates take into consideration breaks and time variance in administration.

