6.3.2 EKG PROCEDURES

To obtain a measure of the heart rate during both stimulation conditions, ECG electrodes as part of the EEG acquisition system are placed on the participant's body. Ideally one electrode will be placed below the left collarbone and a second below the right chest. The EKG will be recorded for the full 40 minutes stimulation session during spontaneous breathing and will be divided into 10 minute intervals for analysis. A standard spectral analysis will be applied to a 10-minute interval, including total power, HF, LF, and VLF. The HF component reflects the parasympathetic modulation of the heart rate.

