11 STATISTICAL PLAN

11.1 STATISTICAL ANALYSIS STRATEGIES

Our study design is a AB/BA crossover and we will ensure a washout effect by scheduling 1-3 weeks between stimulation sessions. A continuous outcome approach will be used to analyze the crossover trial data where carryover effects will be assumed to be equal.

Primary outcome: Use kubios software to analyze HRV over before and after stimulation. A standard spectral analysis will be applied to the pre and post intervals, including total power, HF, LF, and HP. Specifically looking at the HF component since it reflects the parasympathetic modulation of the heart rate. Use a repeated measure ANOVA with factor session (1 vs 2) and factor treatment (active vs sham) (R software). We hypothesize a treatment main effect and with no session effect and no interaction.

Secondary outcome: A Mann-Whitney-Wilcoxon rank-sum testMann Whitney U test (R software) will be performed on the self-report VAS pain scale (nonparametric scale) (from DVPRS) before and after stimulation as well as between sessions to analyze any differences in self-report perceived pain. Grouped ANOVAs and unpaired t-tests may also be used to analyze correlations within other self-report measures

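### With no measure of respiration, the primary HF outcome cannot separate a vagal change from a change in breathing rate

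*Combined protocol and SAP*

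**What the plan says.** The primary alternative hypothesis (Section 2.4.1, Primary Objective) is: "There is a difference in parasympathetic tone in Heart Rate Variability, shown by an increase in high frequency input via spectral analysis on EKG recordings".

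Section 6.3.2 describes the measurement: "The EKG will be recorded for the full 40 minutes stimulation session during spontaneous breathing and will be divided into 10 minute intervals for analysis". It continues: "A standard spectral analysis will be applied to a 10-minute interval, including total power, HF, LF, and VLF". It then gives the interpretation: "The HF component reflects the parasympathetic modulation of the heart rate". Section 11.1 repeats this for the primary outcome: "Specifically looking at the HF component since it reflects the parasympathetic modulation of the heart rate". Neither section attaches a condition about breathing, and no section gives numerical limits for HF.

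During stimulation, in both arms, "participants will stay in a relaxed yet controlled state by watching a nature movie" (Section 4). The planned repeated-measures ANOVA has session and treatment as its only factors. The only covariate named anywhere is heart rate (Section 7.2). The EKG procedures, the visit descriptions (5.2.1 and 5.2.2) and the schedule of events (Appendix A) contain no paced breathing, respiration sensor, EKG-derived respiration, or check that breathing lies inside the HF band.

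The two sections also describe different recordings. Section 6.3.2 analyses 10-minute intervals within the stimulation period; Section 11.1 analyses intervals before and after it.

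**The concern.** Vagal modulation of heart rate appears in the spectrum at the breathing frequency. A fixed HF band captures it only while the person breathes inside that band. Below the lower edge the same modulation is counted as LF, and the stated rule reads this as lost parasympathetic tone although vagal amplitude has not changed.

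So the primary outcome responds to two things, vagal amplitude and breathing rate, and the plan collects nothing that would tell them apart. The trial is meant to supply pilot EKG biomarker data and the basis for later sample sizes. A contrast shrunk by slow breathing, or variance inflated by breathing, would carry into that planning. A difference in breathing between conditions would be reported as a difference in parasympathetic tone.

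**Working it through.** There is no figure in the plan to reproduce. Section 11.2 sets 20 participants without a calculation, and no HF limits, breathing rates, effect size or SD are given. What follows is a range check under stated assumptions.

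**1. Band edge.** Breaths/min = 60 x frequency in Hz. Assumed lower edge 0.15 Hz: 60 x 0.15 = 9. At 0.12 Hz it is 7.2, and at 0.18 Hz it is 10.8.

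**2. How often records fall below the edge.** Assume a mean rate of 12 to 14/min with SD 3. Then z = (9 - 12)/3 = -1.00 to (9 - 14)/3 = -1.67, so 16% to 5% of records, or about 3 to 1 of 20.

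**3. HF at constant vagal amplitude.** Simulated 10-minute heart-period series, respiratory amplitude 30 ms (power 30²/2 = 450 ms²), Welch spectrum, HF 0.15-0.40 Hz.
- White-noise background with a wandering breathing rate, HF relative to 15/min: 0.97 at 12, 0.77 at 10, 0.48 at 9, 0.26 at 8, 0.08 at 7, 0.03 at 6.
- 1/f background: 452 ms² at 15/min, 445 at 10, 123 at 9 (123/452 = 27%) and 7 at 8 (7/452 = 2%). At 8/min LF rises from about 14 to 456 ms², so the power has moved and not vanished.
- Further runs gave 43-49% kept at 9/min and 6-23% at 8. Varying jitter alone, the share kept at 8/min was 3-4% with 2-5% breath-to-breath jitter and 12-21% with 15-25% jitter.

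Overall: roughly 27-49% kept at 9/min and 2-26% at 8/min.

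**4. Slow breathing in both sessions, true vagal power +30%.** True ln difference: ln 1.3 = 0.262. Measured: 0.254 at 9/min, 0.243 at 8, 0.203 at 7, 0.128 at 6. On the untransformed scale that Section 11.1 implies, in units of HF at 15/min, the contrast is 1.29 - 1.00 = 0.29 at 15/min, 0.61 - 0.48 = 0.13 at 9 and 0.33 - 0.26 = 0.07 at 8. It shrinks but keeps its sign.

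**5. Slowing only under active.** A participant at 15/min under sham and 9/min under active, with a true +30%, measures 0.61 of sham, an apparent fall of 39%.

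Let g be the true HF ratio, r the fraction of HF kept after crossing the edge, and q the net share of participants who cross only under active.
- Log scale: the mean is zero when ln g + q ln r = 0, so q = ln g / (-ln r). For g = 1.1, r = 0.1: 0.0953/2.303 = 0.041, or 0.8 of 20. For g = 1.3, r = 0.2: 0.262/1.609 = 0.163, or 3.3 of 20.
- Untransformed scale, assuming equal sham HF in everyone: g[(1 - q) + qr] = 1, so q = (1 - 1/g)/(1 - r). For g = 1.1, r = 0.1: 0.0909/0.9 = 0.101, or 2.0 of 20. For g = 1.3, r = 0.2: 0.2308/0.8 = 0.288, or 5.8 of 20.

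**6. Simulated crossovers.** N = 20, true +30%, breathing-rate SD 3/min between persons and 1.5/min between sessions, paired t-test on ln HF, mean rates 15 / 12 / 10 per minute.
- No treatment effect on breathing: expected ln difference 0.254 / 0.246 / 0.235; chance of a significant positive result 42% / 25% / 16%.
- Active slows breathing by 1/min: 0.187 / 0.009 / -0.147.
- By 2/min: 0.072 / -0.300 / -0.566.
- By 3/min: -0.099 / -0.677 / -1.005.

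**7. Noise on the untransformed scale.** With assumed ln-amplitude SDs of 0.4 between persons and 0.25 between sessions, the SD of the within-person HF difference was 170-250 ms² from breathing alone and 650-820 ms² once ordinary session variation was included.

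**The case against.** A reader might infer that a slow breather by itself reverses the result. The documents do not support that. Each participant is their own control, the film and the relaxed state are the same in both arms, and step 4 shows that slow breathing in both sessions leaves the sign intact. Reversal needs more slowing under active than under sham, across the band edge, and no section says that tACS slows breathing. At a mean of 15/min, slowing of 1 or 2/min still leaves a positive expected contrast. All of this stands.

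A reader might also infer that one or two edge-crossers dominate the error term. That impression comes from the log scale, where values near zero become extreme. Section 11.1 mentions no log transform, and step 7 makes breathing a minority source on the untransformed scale. The power figures in step 6 are likewise log-scale and only indicative. The steepness of the drop at 8/min depends on assumed jitter and noise.

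The plan also outputs LF and total power, so a gross crossing would leave a trace. But nothing in the plan uses that trace to qualify the reading of HF.

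What the objection does not remove: a crossover cancels stable differences in breathing between people, not session-to-session or treatment-related ones. The protocol links alpha oscillations to arousal (Section 2.3) and lists sleepiness among the side effects asked about (Section 10.1), so a breathing difference between conditions cannot be ruled out in advance.

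**Conclusion.** The concern holds in a conditional form. The plan equates HF with parasympathetic tone during uncontrolled breathing and has no respiration information, so it cannot tell a vagal change from a breathing-rate change. A record with unchanged vagal amplitude may keep only 27-49% of its HF at 9 breaths/min and 2-26% at 8.

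The expected consequences are a smaller contrast where people breathe slowly in both sessions and added noise where they cross the edge between sessions. Cancellation or reversal is possible only if breathing slows more under active. In that case, with 80-90% of HF lost, roughly 1 to 3 net crossers of 20 (log scale) or 2 to 6 (untransformed) would offset a true gain of 10-30%. The documents neither show nor exclude this.

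The result rests on an assumed 0.15-0.40 Hz band, inferred from the reference to a standard analysis, and on assumed breathing rates, jitter and background noise. The mechanism does not depend on whether intervals during stimulation or before and after it are analysed, but the breathing conditions in the latter are not described.

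**What to change.** First reconcile Sections 6.3.2 and 11.1 on which EKG intervals form the primary outcome. Then, in both sections:

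- State the HF limits in Hz.
- Derive the breathing frequency of every analysed interval from the recorded EKG, and report it by condition.
- Before unblinding, flag intervals whose breathing frequency lies outside the HF band. Keep them in the analysis: breathing is observed after randomisation and may be affected by treatment, and dropping intervals would break pairs in a 20-person crossover.
- Keep fixed-band HF as the primary measure, and prespecify one sensitivity analysis on all participants with power in a band centred on each interval's own breathing frequency.
- State that if the two analyses disagree, or breathing frequency differs by condition, the result will be reported as a change in HF power and not as a change in parasympathetic tone.

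The cost is SAP wording and some extra signal processing, with no new visits. EKG-derived respiration is itself an estimate and may be noisier during 10 Hz stimulation, so the plan should say how intervals without a usable estimate will be reported.

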6.3.3 PRESSURE PAIN THRESHOLD

The Wagner FDX Algometer will be used for the pressure pain threshold test. Algometers are designed to quantify and document levels of pain sensitivity via pain tolerance measurement. Pressure algometry is a reliable measure of pain in muscle, joints, tendons, and ligaments

Pressure will be applied on both forearms and on the place of most pain on the lower back. The assessment will be done three times in a row at each location and the average of the trials will be used.

EEG PROCEDURES

In addition, in order to detect any change(s) at the neurophysiological level, a resting state EEG will be recorded before and after stimulation during both sessions. This measurement will contribute to the design of novel network-level biomarkers of chronic pain and of response to pain.

6.4 SAFETY MEASURES

We will be monitoring the safety of our participants throughout the study with the following measures. These measures are listed below and can be found in the attached documents.

- A. A stimulation adverse effects questionnaire used in previous studies (IRB #14-1622, #14-3285, and #14-0600) will be administered at the end of each stimulation session. This questionnaire will be used as a safety measure and to collect data on participant experience. Please see *10.1 Safety Parameters* for more information.
- B. More as needed. Refer to previous IRB applications as needed.

6.5 LABORATORY EVALUATIONS

6.5.1 SCREENING LABORATORY EVALUATIONS

A urine pregnancy test will be performed for any female participant who is unable to confirm pregnancy status.

INSTRUCTIONS FOR SPECIMEN PREPARATION, HANDLING, AND STORAGE. For this laboratory evaluation, results are available after only a few minutes. Once the results are clear, the researcher will make a note and the sample will be disposed. All samples will be handled using single-use disposable medical gloves.

6.5.2 SALIVA SAMPLE

We will be collecting a saliva sample during the first visit. This sample will be used to test for a single nucleotide polymorphism in the BDNF gene whose presence may have an influence on effectiveness of brain stimulation. Within the central nervous system, BDNF regulates survival, proliferation, and synaptic growth as well as directly influences synaptic plasticity in the adult human brain (Antal et al., 2010a). Egan et al. (2003) demonstrated that Val66Met, a single nucleotide in the BDNF gene, has function consequences in healthy humans, including decreased episodic memory and hippocampal inducing a reduction in recall capacity. This polymorphism is common in over one third of the Caucasian population (65% Val66Val to 35% Val66MET) (Pezawas et al, 2004; Hariri and Weinberger, 2003). Kleim et al. (2006) found that individuals with the Val/Val polymorphism respond to tDCS and transcranial magnetic stimulation (TMS) treatments with expected change, whereas, individuals expressing Val/MET allele do not. These authors indicate the difference to be caused by the impairment in synaptic plasticity caused by the Val/MET allele. These findings suggest that individual efficacy of treatments using brain stimulation may be partially genetically predetermined and should be taken into account when performing such procedures. Accordingly, we will conduct genotyping of all participants in this study in order to assess BDNF status. We will perform exploratory analyses in which we group participants by BDNF status. A saliva sample will also test for levels of progesterone, estradiol,

INSTRUCTIONS FOR SPECIMEN PREPARATION, HANDLING, AND STORAGE. The saliva sample will be collected using 2mL DNA collection kit from DNA Genotek. Before sample collection, it is imperative that the participant does not eat, drink, smoke or chew gum for at least 30 minutes before providing a sample. Once the participant provides the 2mL sample, the collection tube is closed and a liquid from the lid will be released into the tube. The original lid will be removed and replaced with a small cap and the tube will be agitated for 5 seconds. The sample is then returned to the plastic packaging and labeled with the date of collection, the study name, and the participant ID. These samples are kept in a secure location until the completion of data collection.

7 STUDY INVESTIGATIONAL PRODUCT

We will be using the XCSITE100 stimulator designed in the [name] Lab for investigational purposes. The device is not implanted and has not been designed for or being used to support or sustain human life. This device does not have a potential for serious risk to the health, safety, or welfare of the participant. There has never been an instance of serious side-effect reported due to the use of transcranial brain stimulation. Previous studies in the [name] lab that used comparable devices (i.e., the commercial, CE-certified Neuroconn Plus stimulator) have always been classified as “non-significant risk” by the full UNC IRB. The Neuroconn Plus stimulator and the XCSITE100 stimulator are electrically equivalent and provide the same stimulation.

The XSCITE100 is the first non-invasive brain stimulator designed for research purposes to provide an active sham for tACS and record the stimulation output for later validation. This stimulator may apply either tDCS or tACS for up to 40 minutes (2400 seconds) with appropriate current ramp-up at the beginning of stimulation and ramp-down at the end of stimulation. Both tDCS and tACS may be applied for currents between 100 μ A and 2 mA (peak-to-peak for tACS).

The stimulator has two main components:

1. Android tablet with user interface application (i.e., App)
2. Stimulator with:
 - a. Microprocessor
 - b. Function generator chip
 - c. Voltage controlled current source
 - d. Safety circuitry

To ensure appropriate blinding for each stimulation session, there are designated unblinded individuals to ensure the appropriate stimulation parameters are applied to each participant. These individuals will not interact with participants and will only be involved with the creation of a study file and validation of stimulation waveform.

7.1 SAFETY FEATURES

[figure not shown]
Current Sensor Circuit. A 33.2 Ω sense resistor is placed in series with the stimulation electrodes on the high side. Since high-side current sensing is used, any short circuit of the electrode terminals to ground will be detected. The stimulation current flows through this resistor and creates a voltage. The voltage across this resistor is sensed and amplified by the AD628 difference amplifier. The gain of the difference amplifier is set to 9.9039. The current sensor voltage is then shifted before it is read by the microprocessor and the hardware current safety feature.

Voltage Sensor Circuit. The differential voltage across the electrodes is measured so that the impedance can be calculated. The voltage is measured by buffering the positive electrode and negative electrode each with a unity gain op-amp circuit. The voltage output is then shifted before it is read by the microprocessor using the same level shifting circuit described in the current sensor section.

The device is equipped with 4 different stages of safety precautions, all of which protect the participant from high currents. The stages are as follows:

1. **AUTOMATIC SOFTWARE CURRENT CUTOFF.** The output of the current sensor described above is read by a microprocessor, which compares the reading to a value of ± 3 mA peak. If the current exceeds these limits, stimulation is stopped, a relay in series with the electrode is opened, and the power supply used for stimulation is turned off. The user is then given the option to investigate the issue, and cancel or resume the test. Since high-side current sensing is used (described above), any short circuit of the electrode terminals to ground will be detected.
2. **AUTOMATIC HARDWARE CURRENT CUTOFF.** The output of the current sensor is fed into a pair of comparators which detect if the current exceeds ± 4.5 mA. If so, the fault is latched such that the relay in series with the electrodes is opened. Additionally, the microprocessor is notified of this instance through an interrupt. Upon this interrupt, the microprocessor immediately stops stimulation and the power supply used for stimulation is turned off.

Figure 1. Example of a successful hardware cutoff function

3. **PERMANENT HARDWARE CURRENT CUTOFF.** A 5 mA fast-acting fuse is in series with the electrode connector. If the above two over-current detection methods fail, the fuse will blow, and the stimulator will no longer be electronically connected to the device.
4. **POWER SUPPLY FUSE.** Finally, if for no other reason the entire device draws too much current, the main power supply fuse is blown. This fuse is sized with a cutoff of 200% of steady-state operating current.

7.2 PREPARATION AND ADMINISTRATION OF STUDY INVESTIGATIONAL PRODUCT

After participants have completed the daily questionnaire, they will be comfortably seated. The researcher(s) will first measure their head using the 10-20 system for accurate electrode placement. Participants will then be fitted with the 3 electrodes for stimulation. Electrodes will be applied using Ten20 conductive paste, 5x5cm electrodes placed over F3 and F4 with a 5x7cm placed over CZ as a return electrode. The participant will be in a relaxed yet experimentally controlled state by watching "Reefscape". One session of stimulation will be performed per day for 40 minutes. For the 10 Hz tACS stimulation, there will be a 10 second ramp-in and ramp-out with 40 minutes of stimulation for a total of 2420 seconds. Stimulation waveforms are sine-waves with a peak-to-peak amplitude of 2 mA. The sham stimulation will include 10 seconds of ramp-in to 1 minute of 10 Hz tACS with a ramp-out of 10 seconds for a total of 80 seconds of stimulation. As a covariate, heart rate will be recorded throughout stimulation.

Stimulation devices will be programmed and codes will be randomized to one of the two experimental arms. Researchers will enter the participant-specific code into the App that controls the stimulation and monitor participants during the 40 minutes of stimulation.

The study coordinator and/or the research assistant will be thoroughly trained and have trainings documented on the transcranial stimulation device and will be present during all stimulation sessions. To monitor side effects of stimulation, a daily questionnaire will be administered after each stimulation session.

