5.2 STIMULATION SESSIONS

5.2.1 DAY 1 OF STIMULATION (VISIT 1 CONTINUED)

Prior to starting any study procedures, female participants will be asked to take a urine pregnancy test to ensure continued eligibility. The 5xSST, FTF, and pressure pain threshold test will be administered before stimulation. A resting state EEG will be recorded for 5 min before and after stimulation. The participant will receive 40 minutes of sham or 10 Hz tACS stimulation (as per the initial randomization) while watching “Reefscape”. The stimulation will be followed by the pressure pain threshold, 5xSST, FTF, stimulation adverse effects questionnaire and perceived improvement ending the session.

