5.2.2 DAYS 2 OF STIMULATION (VISIT 2)

Prior to starting any study procedures, female participants will be asked to take a urine pregnancy test to ensure continued eligibility. The ODI, DVPRS, 5xSST, FTF, and pressure pain threshold test will be administered before stimulation. A resting state EEG will be recorded for 5 min before and after stimulation. The participant will receive 40 minutes of sham or 10 Hz tACS stimulation (as per the initial randomization) while watching “Reefscape”. The stimulation will be followed by the pressure pain threshold, 5xSST, FTF, stimulation adverse effects questionnaire and perceived improvement ending the session.

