8.3 REFERRALS FOR MEDICAL FOLLOW-UP OR PSYCHOLOGICAL COUNSELING

There is a purely theoretical likelihood that stimulation of neuronal circuits can lead to epileptic discharge. To minimize this occurrence, we screen and exclude patients with personal and family history of neurological conditions from the study. If abnormalities or a seizure is witnessed during the course of the study, a referral will be made to the UNC Department of Neurology for follow-up. In the theoretical event that a seizure is witnessed that involves the loss of consciousness, the patient will be told not to operate a motor vehicle until cleared by the DMV.

We will be using the Hamilton Psychiatric Rating Scale for **Depression** (HAM-D) to assess depression and suicide risk at the initial session. Inclusion criteria states that the patient must be low suicide risk, potential participants that have an above “low risk” designation that is currently clinically relevant will not be eligible for the study.

To ensure participant comfort, a study coordinator or research assistant will periodically check in with the participant about any side-effects he/she may be experiencing during each stimulation session. Following the conclusion of the stimulation session, the participant will receive an Adverse Effects Questionnaire to report on any of the side-effects he/she may have experienced. This questionnaire reports side-effects on a likert scale (1=Absent, 2=Mild, 3=Moderate, 4=Severe). If the participant reports side-effects of Moderate to Severe intensity, a study coordinator or research assistant will discuss the side-effects experienced and note this response. The medical monitor will be contacted based on the reported intensity on the Adverse Events Questionnaire and the participant’s verbal confirmation of intensity.

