APPENDIX B: AE REPORT FORM

Adverse Effects Report:

Reasons for Report (adverse event, time, date and place of occurrence if available):

1. What do we already know about the therapy?
 - a.
2. What is the temporal relationship of the AE to the study therapy?
 - a.
3. Does the AE improve or disappear when the therapy is stopped?
 - a.
4. Is the AE a worsening of baseline symptom(s)?
 - a.
5. Is the AE a result of an underlying concurrent medical condition(s) or concurrent medication(s)?
 - a.
6. Additional Information provided by research team
 - a.

Research team member signature _____

Date _____

Co-Investigator:

Steps to be taken (if applicable)

Co-I signature _____

_____ Date _____

PI Comments:

Steps to be taken (if applicable)

PI signature

Date

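### Section 7.2's daily questionnaire is undefined and has two timings, and no pre-stimulation rating of the side-effect items is scheduled

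*Combined protocol and SAP*

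**What the plan says.** Section 7.2 uses one term at two points. Before electrode placement: "After participants have completed the daily questionnaire, they will be comfortably seated". At the end of the same section: "To monitor side effects of stimulation, a daily questionnaire will be administered after each stimulation session". The content of the first form is not stated, and the term does not appear in the visit descriptions, the lists of measures or Appendix A.

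Elsewhere the side-effect form comes after stimulation:

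- Section 5.2.1: "The stimulation will be followed by the pressure pain threshold, 5xSST, FTF, stimulation adverse effects questionnaire and perceived improvement ending the session". Section 5.2.2 gives the same post-stimulation order for visit 2.
- Section 6.4: the form "will be administered at the end of each stimulation session".
- Section 8.3: "Following the conclusion of the stimulation session, the participant will receive an Adverse Effects Questionnaire". Section 8.2.2 agrees.
- Section 10.1: at the end of each session, and also at a 4 week follow-up visit that Appendix A does not contain.

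The pre-stimulation list at visit 2 has no symptom rating: "The ODI, DVPRS, 5xSST, FTF, and pressure pain threshold test will be administered before stimulation". Appendix A ticks a stimulation questionnaire once per stimulation visit without saying where in the visit it falls. Its baseline row is an unfilled placeholder, ticked for the first visit only.

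Section 10.1 describes the form as 14 named items plus an open one. Each is rated 1 (absent) to 4 (severe) for the session, and a separate 5-point scale records how far the participant thinks the effects relate to stimulation. Section 10.2.1 and Appendix B item 4 ask whether an adverse event (AE) worsens a baseline symptom.

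**The concern.** Several listed items are not specific to stimulation. People with chronic low back pain may arrive with a headache, neck pain, sleepiness or poor concentration. If such a symptom lasts through the 40-minute session, a truthful participant will report it on a form that asks about the session. Nothing scheduled beforehand distinguishes it from a symptom that began under the electrodes.

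Two uses of the data are affected. The first is the tolerability rate. The study summary gives feasibility as an aim, and section 8.1 expects the results to support proposals for a large trial, so the absolute rate under tACS is likely to be carried forward. The second is the classification of single events. Section 10.2.1 calls an event associated when it is linked in time to the therapy and nothing else explains it, and that depends on whether the symptom came first.

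There is also a conduct problem. Staff following section 7.2 would give a form before stimulation that staff following section 5.2 would not recognise. A baseline missed at a session cannot be recovered later.

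**Working it through.** The plan states no figure on this point, so there is none to reproduce. The check has three steps.

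**1. Does any section schedule a rating of the side-effect items before stimulation?**

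| Place | Before stimulation | After stimulation |
|---|---|---|
| 7.2 | Daily questionnaire, content not stated | Daily questionnaire, for side effects |
| 5.1.2 and 5.2.1 (visit 1) | Questionnaires, physical tests, pressure pain threshold, EEG | Side-effect form |
| 5.2.2 (visit 2) | ODI, DVPRS, physical tests, pressure pain threshold, EEG | Side-effect form |
| 6.4, 8.2.2, 8.3, 10.1 | None for these items | Side-effect form |
| Appendix A | None identifiable | One tick per visit, order not given |

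No section does. The only candidate is the first form in section 7.2, and nothing shows what it asks.

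**2. Do other baseline data fill the gap?**

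- ODI and DVPRS, before both stimulations, cover disability, pain and the impact of pain on daily living. They are not ratings of the listed side effects.
- DASS-21 covers the past week (6.1) and is described at visit 1 only (5.1.2).
- Appendix A reviews medical history at phone screening and the first visit, not at the second, which is 1-3 weeks later.
- Section 10.2.1 treats medical conditions noted at the initial session as baseline. That covers known conditions, not a headache on the day.
- Check-ins during stimulation (8.2.2, 8.3, 10.1) start after the baseline moment has passed.

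These data partly cover pain, disability, mood and known conditions. They do not give a same-day baseline for the transient items.

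**3. What does this do to the rates?** For one item, let p be the probability that it is present on arrival. Let q_A and q_S be the probabilities that it starts during an active or a sham session when it was absent on arrival. Assume that an arrival symptom lasts through the session and is reported, and that p is the same for both conditions. Randomised order gives the latter in expectation if nothing carries over between visits. Then:

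- Raw rate in condition c: R_c = p + (1 - p)q_c.
- Rate of new symptoms: (1 - p)q_c.
- Excess of the raw rate over the new-symptom rate: R_c - (1 - p)q_c = p, in each condition.
- Raw contrast: R_A - R_S = (1 - p)(q_A - q_S), which equals the contrast in new symptoms.

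The absolute rate is therefore too high by p in both conditions, while the expected active-sham difference is not biased. With 20 participants and 40 sessions, arrival symptoms will not balance exactly, so they add noise. A count of symptoms present also misses the worsening of one already there. The documents give no value for p.

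**The case against.** The strongest reply is that the plan already has the safeguards that matter. Every participant has a sham session. Relatedness is rated separately, starting from no relation. AEs are recorded whatever their relation to tACS, and the principal investigator and co-investigator judge association. Conditions noted at the initial session are not reported as AEs. Callers treated for neurological conditions such as migraine are screened out, and low depression is required. Neither hypothesis concerns side effects, and section 11.1 plans no side-effect comparison. The first form in section 7.2 may simply be the pre-session self-reports, in which case only a name needs tidying.

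Much of this stands, and it rules out several stronger readings that a reader might infer:

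- **That arrival symptoms are counted as stimulation effects.** They can be recorded as session symptoms. Attribution is a separate step, with its own rating and judgement.
- **That Appendix B item 4 cannot be answered.** It is free text. Staff can use the baseline data for pain, disability, mood and known conditions, and can ask the participant. Only the transient items lack a prospective record.
- **That section 7.2 contradicts the other sections on when side effects are rated.** Nothing shows that its first form rates side effects. What is established is an undefined term with two timings.
- **That contact with the medical monitor follows from the raw score alone.** Section 8.3 says "The medical monitor will be contacted based on the reported intensity on the Adverse Events Questionnaire", but the sentence goes on to require the participant's verbal confirmation as well, and staff first discuss moderate or severe effects with the participant.

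What the reply does not remove is the missing same-day baseline. The sham contrast cannot classify a single event or correct the absolute rate, and the relatedness item records a blinded participant's belief, not the time of onset.

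**Conclusion.** The point holds as a gap that is cheap to close. It does not invalidate the trial. The daily questionnaire in section 7.2 is undefined and has two timings, and no section schedules a pre-stimulation rating of the side-effect items. For transient symptoms, the absolute side-effect rate can be inflated in both conditions, and Appendix B item 4 and the association judgement rest on recall.

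Under the assumptions in the working, the inflation equals the share of sessions that begin with the symptom. The documents do not give that share, so no size is claimed. The expected active-sham difference is not biased, and the primary and secondary hypotheses are unaffected. The conclusion about the missing baseline rests on the schedule alone. If the first form in section 7.2 does rate these symptoms, the gap largely closes, but the protocol would still need to say so.

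**What to change.** 1. Define the daily questionnaire in section 7.2, or give the two forms different names. Reconcile that section with 5.2.1, 5.2.2, 6.4, 10.1 and Appendix A, including the 4 week visit that appears only in 10.1.
2. Immediately before stimulation at both visits, rate current severity (1-4) on the items that can be present on arrival, such as headache, neck pain, sleepiness and trouble concentrating. Leave out stimulation-specific sensations and the two mood items, which already ask about change.
3. Report by condition the symptoms that are new or worse than the pre-rating, alongside the raw post-stimulation ratings.
4. Use the pre-rating to inform Appendix B item 4.
5. Leave the stopping and medical-monitor contact rules unchanged.

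The cost is an estimated 2-3 minutes per visit. Over 20 x 2 = 40 sessions that is 80 to 120 minutes for the whole trial, plus an entry in Appendix A, with no extra staff. The downside is priming: asking about a symptom beforehand may change how often it is reported afterwards. Even if equal in both conditions, priming may affect the absolute rates, so the report should state that a pre-rating was taken.
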